## 2.1.2. Safety data

Study period	Treatment groups	Analysis populations	Imputation method
“Chapter 1”: Period 1, up to Week 12	The 7 original groups: 

– Placebo

– GLPG0634 q.d. dosing groups:

• 50 mg q.d.

• 100 mg q.d.

• 200 mg q.d.

– GLPG0634 b.i.d. dosing groups:

• 25 mg b.i.d.

• 50 mg b.i.d.

• 100 mg b.i.d.

	Safety: all subjects randomized and exposed at least once.	Observed-case only (no imputation)

Study period	Treatment groups	Analysis populations	Imputation method

“Chapter 2”: Periods 1+2 together (full 24 weeks period)
	
The 11 groups of the second study period, taking into account treatment switches:
 
 
– Subjects starting on placebo                             
 
• Continued placebo
 
• Switched to 100 mg q.d.
 
• Switched to 50 mg b.i.d.
 
 
 
– GLPG0634 continued dosing in responders                             
 
• 50 mg q.d.
 
• 25 mg b.i.d.
 
 
 
– GLPG0634 continued dosing in non-responders                             
 
• 50 mg q.d. increased to 100 mg q.d.
 
• 25 mg b.i.d. increased to 50 mg b.i.d.
 
 
 
– GLPG0634 continued q.d. dosing groups                             
 
• 100 mg q.d.
 
• 50 mg b.i.d.
 
 
 
– GLPG0634 continued b.i.d. dosing groups                             
 
• 200 mg q.d.
 
• 100 mg b.i.d.
 
 
 
 
For the subjects in the placebo and low dose groups who discontinued prior to Week 12: they will be included in the “continued placebo”, “continued 25 mg b.i.d.” and “continued 50 q.d.” groups.
 
Note that AEs will be presented overall, but also split up in the two study periods.
	
Safety: all subjects randomized and exposed at least once during the study.
	
Observed-case only (no imputation)

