**Table 14.1.1.8: Subject disposition up to study end: Tabulation of the trial termination reasons**

Repeat table for the second period of the study.

Population: safety subjects who entered the second part of the study.

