### 12.1.5. Calculation of Percentages

All percentages will be calculated against the total number of subjects that are still in the study in that particular analysis period.

### 12.1.6. Tables up to Week 12

No formal inferential statistics (p-values) will be derived.

An as-treated analysis will be performed. All tabulations and listings will present treatments rather than analysis periods.

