### 12.1.7. Tables over the whole 24 weeks period

The same tables will be created for the full 24 weeks period of the study, using the 11 groups as specified in section 2.4.

All tables will be created for 3 analysis periods: “first 12 weeks”, “second 12 weeks”, and “full 24 weeks” as defined in section 3.2.

Population: Safety.

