#### **Table 14.3.1.16: Treatment-emergent adverse events over the whole study: Summary table**

Tabulation per treatment of the number and percentage of subjects with the following:

- Subjects with at least one treatment-emergent adverse event (TEAE)
- Subjects with at least one serious TEAE
- Subjects who died (treatment-emergent)
- Subjects with at least one mild TEAE as worst intensity
- Subjects with at least one moderate TEAE as worst intensity
- Subjects with at least one severe TEAE
- Subjects with at least one TEAE that was considered treatment-related
- Subjects with at least one treatment-emergent SAE that was considered treatment-related
- Subjects with at least one TEAE for which the study treatment was temporarily stopped
- Subjects with at least one TEAE for which the study treatment was permanently stopped
- Subjects with at least one TEAE flagged as an individual stopping criterion by the investigator
- Subjects with at least one TEAE that has not resolved.

Population: safety.

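### Whole-study safety tables put all pre-Week 12 discontinuers from placebo and the 50 mg/day arms in the continued columns, so stop-type rows and exposure are not comparable across columns

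*SAP*

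**What the plan says.** SAP 2.1.2 specifies, for the full 24-week safety analysis, "The 11 groups of the second study period, taking into account treatment switches". Placebo splits into continued placebo and two switched columns. Each 50 mg/day arm splits into a continued and an increased column. The 100 and 200 mg/day arms stay whole. The low-dose continued columns are headed "GLPG0634 continued dosing in responders".

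The same section then deals with subjects who never reached the Week 12 decision: "For the subjects in the placebo and low dose groups who discontinued prior to Week 12: they will be included in the" columns for subjects who stay on their randomised treatment, one for each of these three arms.

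For adverse events, SAP 12.1.7 states: "All tables will be created for 3 analysis periods", namely the first 12 weeks, the second 12 weeks and the full 24 weeks. The denominator rule in SAP 12.1.5 is: "All percentages will be calculated against the total number of subjects that are still in the study in that particular analysis period". Table 14.3.1.16 includes the row "Subjects with at least one TEAE for which the study treatment was permanently stopped", and another for events flagged as an individual stopping criterion. Table 14.1.4.2 (SAP 7.8.3) reports whole-study exposure by the same sequences.

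**The concern.** A subject must reach Week 12 to be switched or increased, so those columns cannot contain anyone who left before Week 12. The allocation rule sends every such subject from three arms to the continued columns. In the first-12-weeks tables the three placebo-origin columns all describe subjects taking placebo, yet only one of them can show a pre-Week 12 discontinuation. That difference comes from how the columns are built, not from any treatment.

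Continued placebo is also the only placebo column that runs to Week 24, so readers will naturally use it as the reference. Its stop-type rows and exposure summaries mix Week 12 responders with subjects who had no Week 12 classification. The responder heading on the two low-dose columns has the same fault.

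The efficacy plan is more careful. Its second-period analysis excludes subjects who discontinued before Week 12 (SAP 2.1.1 and 4.4.5), and SAP 4.5.1 warns that comparisons after Week 12 need care. SAP 4.5.2, the safety counterpart, has no such warning.

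**Working it through.** **Inputs from the documents.** Each arm has 85 subjects. Protocol 8.8.2 assumes a placebo ACR20 of 20-40%. Its detectable active rates are 48% and 70% (90% power) and 45% and 66% (80% power). These figures reproduce: a two-sided chi-square test at 0.05/6 with 85 per arm gives power of 89.8% (20 v 48), 91.3% (40 v 70), 80.9% (20 v 45) and 78.4% (40 v 66). The plan states no discontinuation rate and no expected size for the continued columns.

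**Assumptions.** Dropout before Week 12 is d1 = 3-15% of the randomised arm. Dropout after Week 12 is d2 = 0-5% of those who reach it, the same in continued and switched subjects. The share of the randomised arm that continues unchanged is s. ACR20 rates stand in for s, and the 50 mg/day arms are taken to respond at the design's active rates.

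**Formulas.**
- Continued column size: 85(s + d1)
- Continued column rate: (d1 + s·d2)/(s + d1)
- Randomised-arm rate: d1 + (1 − d1)·d2
- Switched column rate: d2

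If the events occur only among early discontinuers (d2 = 0), the ratio of column rate to arm rate is 1/(s + d1). If AE-related stops are a constant fraction of all stops, that fraction cancels, so the ratio also applies to AE-stop rows.

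**One case with identical dropout in every arm: d1 = 10%, d2 = 5%.**
- Randomised arm, and so any 100 or 200 mg/day column: 0.10 + 0.90 × 0.05 = 14.5%
- Continued placebo at s = 30%: (0.10 + 0.015)/0.40 = 28.8%, on 34 subjects
- Continued 50 mg/day at s = 48%: (0.10 + 0.024)/0.58 = 21.4%
- Continued 50 mg/day at s = 70%: (0.10 + 0.035)/0.80 = 16.9%
- Any switched column: 5%

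Equal underlying behaviour thus produces clearly different column figures.

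**Ranges over d1 = 3-15% and d2 = 0-5%.**

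| Arm | s | Column size | Ratio to arm rate |
|---|---|---|---|
| Placebo | 20% | 20-30 | 2.2-4.4 |
| Placebo | 30% | 28-38 | 1.7-3.0 |
| Placebo | 40% | 37-47 | 1.5-2.3 |
| 50 mg/day | 45% | 41-51 | 1.4-2.1 |
| 50 mg/day | 48% | 43-54 | 1.35-1.96 |
| 50 mg/day | 66% | 59-69 | 1.16-1.45 |
| 50 mg/day | 70% | 62-72 | 1.13-1.37 |

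The switch rule (Protocol 8.1) uses only the two joint counts, which is easier to meet than ACR20. The true s is therefore at least the ACR20 rate, and the ratio falls as s rises, so these are upper-end figures. The 20% row is the floor of the design's placebo range, and the size below rests on 30-40%. In subjects, 3-15% of 85 is about 3 to 13 early stops per arm, and AE-related stops are a subset of those.

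**The case against.** The allocation has a rationale. Early discontinuers took only placebo or the low dose, so placing them under the treatment they took fits the as-treated principle in SAP 2.4.1, and it keeps every exposed subject in the tables. Safety is descriptive, with no p-values. SAP 2.1.2 adds: "Note that AEs will be presented overall, but also split up in the two study periods". Under the denominator rule, the second-12-weeks AE tables leave early discontinuers out. The placebo-controlled view up to Week 12 uses the seven original arms and is clean.

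All of this stands and limits the point. It does not repair the 11-column first-12-weeks and full-24-weeks rows, or whole-study exposure.

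Three stronger readings are tempting, and the documents do not support them.
- *That all-cause discontinuation is roughly doubled in the 24-week columns.* No planned table pools it that way. Trial termination is tabulated by period, and the later table is limited: "Population: safety subjects who entered the second part of the study". A factor of two also needs a dropout rate and a continuing share that the plan does not give, and it fits placebo better than the 50 mg/day arms.
- *That the rule makes the switched columns look safe.* They contain no pre-Week 12 stops under any sequence definition. The rule changes only the continued columns.
- *That the tables are biased in favour of GLPG0634.* Two of the three inflated columns are GLPG0634 columns. For overall AE incidence and worst-case labs the direction is uncertain, because early discontinuers also have shorter exposure and fewer visits.

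**Conclusion.** The concern holds in a limited form. In the first-12-weeks and full-24-weeks versions of the 11-column tables, stop-type rows (TEAEs leading to permanent stop, stopping-criterion events) are inflated in the three continued columns, and whole-study exposure there is shortened. Those columns cannot be compared with the switched columns, or with the 100 and 200 mg/day columns.

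Under the assumed dropout, the inflation over the randomised-arm rate is about 1.5-3.0 for placebo with 30-40% continuing. It is about 1.1-2.1 for the 50 mg/day arms at the design's active response rates. Both ranges are upper-end and conditional on values the documents do not state.

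The up-to-Week 12 tables by original arm, the second-12-weeks AE tables and the period-split termination tables are unaffected. The primary endpoint is untouched. This is a fault of presentation, worth correcting because the correction is cheap.

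**What to change.** In SAP 2.1.2, replace the allocation rule. Show subjects from placebo, 50 mg q.d. and 25 mg b.i.d. who discontinued before Week 12 in their own columns, labelled as discontinued before Week 12, in the whole-study safety and exposure tables. Keep them in the Safety population. The responder heading on the low-dose continued columns then becomes accurate. In the worked case (d1 = 10%, d2 = 5%), the continued and switched columns would both show 5%, with the early stops visible beside them.

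Add a footnote that the 100 and 200 mg/day columns still include their own early stops, so a comparison with them needs the columns of each original arm added together. Optionally, add exposure-adjusted AE incidence by treatment taken at onset.

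Do not restrict these tables to subjects who entered the second period. That would drop early SAEs from the 24-week tables and largely repeat the planned second-12-weeks AE view.

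The cost is SAP wording, matching mock tables and up to three extra columns in tables that are already wide. No new data are needed.

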## **2.2. FURTHER ANALYSIS POPULATIONS**

### **2.2.1. All Screened Subjects Population**

All subjects who signed an informed consent form.

### **2.2.2. All Randomized Population**

All subjects randomized into the study.

## **2.3. HANDLING OF UNBLINDED SUBJECTS**

### **2.3.1. Safety population**

In case a particular subject would be unblinded (e.g., in case of an SAE), all safety data of this subject recorded in the database will still be included in the safety analysis.

### **2.3.2. Intent to Treat Population**

In case a particular subject would be unblinded (e.g., in case of an SAE), all efficacy data of this subject up to the point of unblinding will still be included in the ITT efficacy analysis. Recorded efficacy data from the moment of unblinding onwards will be disqualified from the analysis. Such data will still be part of the listings, but will be labeled as use=no. Missing data after the moment of unblinding will be imputed using the same rules as used for other subjects.

### **2.3.3. Per Protocol Population**

In case a particular subject would be unblinded (e.g., in case of an SAE), all efficacy data of this subject up to the point of unblinding will still qualify for the per-protocol efficacy analysis selection according to the above rule of excluding critical protocol deviations. Recorded efficacy data from the moment of unblinding onwards will be disqualified from the analysis. Such data will still be part of the listings, but will be labeled as use=no. Missing data after the moment of unblinding will be imputed using the same rules as used for other subjects.

## **2.4. TREATMENT GROUPS**

### **2.4.1. Randomized versus Actual Treatment**

For efficacy parameters, the treatment group as assigned by the randomization will be used in the analysis (i.e., as-randomized analysis, considered closest to a worst-case intention-to-treat principle).

For safety parameters, the treatment that was actually used by the subject will be applied in the analysis (i.e., as-treated analysis, considered the fairest worst-case method to allocate potential safety problems to the treatment that was actually used). Such an as-treated analysis will only be done in case more than 20% of the actually used study drug was different than planned and is in a higher dose than planned. If the subject uses less than 20% of incorrect kits or the incorrect kit is a lower dose, then an as-randomized analysis will be applied. The

“20%” mentioned here is over the related study period: period 1 only, or full periods 1+2 combined, or period 2 only (for AE), depending on the analysis chapter.

During the second part of the study: if the subject passed the re-randomization visit (Week 12) but it is unknown whether the subject actually used any study drug during the second part of the study, then it is assumed that the subject used at least one dose of study drug during the second part. If the subject passed the re-randomization visit and it is known that the subject did not take any study drug during the second part of the study, then the re-randomization will be ignored and the subject will only have a study part 1 in the analysis.

Differences between as-treated and as-randomized will be flagged in the listing on subject allocation.

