**Table 14.2.1.1.3: ACR20: Exploratory pairwise comparisons between regimens within each daily dose level**

Logistic regression model at each time point, modeling the responders. Factors in the model are: regimen, dose, regimen\*dose interaction, region, and previous use of biologics. Placebo

subjects will not be used in this model (as there is no q.d./b.i.d. regimen available for placebo). The regimen\*dose interaction will be removed from the final model when not significant at level 0.10 (two-sided type-III p-value). Regimen will have 2 categories: q.d. or b.i.d. Dose will have 3 categories, corresponding to the total daily dose: 50 mg/day, 100 mg/day, or 200 mg/day.

Per time point, the table will present:

- Per dose: difference in percentage responders of q.d. versus b.i.d. within the same dose level (50, 100 or 200 mg/day), together with a 95% confidence interval of this difference (as provided by SAS PROC FREQ).
- Per group: p-value for pairwise comparison of q.d. versus b.i.d. These p-values will be presented both as uncorrected p-values, and are derived as contrasts within the overall logistic regression model. As this is a purely exploratory analysis, no adjustment for multiplicity will be performed.

The “raw” SAS PROC output must be provided in a statistical appendix listing.

The table will show:

- NRI in ITT and in per-protocol
- LOCF in ITT and in per-protocol
- observed-case in ITT (inferential statistics at Week 12 only).

Table to be created for the Week 12 interim analysis as well, cut off at Week 12. ITT only.

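### The as-treated safety rule in SAP 2.4.1 moves subjects upward only: a subject who took mostly or only lower-dose or placebo kits stays in the randomised higher-dose column

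*SAP*

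**What the plan says.** SAP 2.4.1 opens with the principle: "For safety parameters, the treatment that was actually used by the subject will be applied in the analysis". It gives the reason that this is "considered the fairest worst-case method to allocate potential safety problems to the treatment that was actually used".

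The next sentences limit it. A subject is moved to the actual treatment in one situation alone, namely where "more than 20% of the actually used study drug was different than planned and is in a higher dose than planned". Then, if fewer than 20% of kits were wrong "or the incorrect kit is a lower dose, then an as-randomized analysis will be applied". The 20% is counted over the study period that the analysis covers. Differences between as-treated and as-randomised allocation are flagged in the listing of subject allocation (Listing 16.2.1.1).

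SAP 12.1.6, which introduces the adverse event tables up to Week 12, says "An as-treated analysis will be performed" and does not repeat the restriction. SAP 2.4.2 adds a column pooling all GLPG0634 groups for safety up to Week 12.

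**The concern.** The principle and the working rule give different answers for the same subject. The principle follows the drug taken. The rule follows it only when the error went up in dose.

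The worst-case rationale covers one half of the problem. Keeping a subject's events in the higher-dose column cannot hide events from that dose. Keeping a subject who had less or no exposure in that column's denominator, however, can lower its rates. An event that occurred on placebo kits is also charged to the active arm and to the pooled GLPG0634 column. The net direction cannot be predicted.

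What is at stake is how cleanly the safety tables show the relation to dose. SAP 6.2 plans a Week 12 interim output, with adverse event tables, to support preliminary phase III dose selection. That output contains no listings, so the allocation flags would not be visible there. The list of changes after the interim lock (SAP 6.3.2) records no change to this rule, so I assume that it also applied at the interim.

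**Working it through.** **Step 1: the rule, case by case.** The plan states no figure to reproduce here, so the check is a reading of SAP 2.4.1. Take a subject whose wrong kits exceed 20% of the drug used.

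| Wrong kits were | Principle | Working rule |
|---|---|---|
| Higher dose | Actual treatment | Actual treatment |
| Lower dose | Actual treatment | As randomised |
| Placebo, in a GLPG0634 arm | Actual treatment | As randomised (zero is a lower dose) |
| Other regimen, equal daily dose | Actual treatment | As randomised, if dose means total daily dose |

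The two conditions in the as-randomised sentence are alternatives, so the lower-dose row holds even when 100% of the kits were wrong. The last row rests on the preceding sentence, which allows as-treated allocation only for a higher dose. SAP 2.4.1 does not define dose. The SAP's regimen model for ACR20 (Table 14.2.1.1.3) does: "Dose will have 3 categories, corresponding to the total daily dose: 50 mg/day, 100 mg/day, or 200 mg/day". On that usage, 100 mg q.d. and 50 mg b.i.d. are the same dose and neither is higher.

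**Step 2: a full swap.** Suppose one placebo subject and one 200 mg q.d. subject receive each other's kits throughout, with 85 per arm (Protocol 8.5.4). The placebo subject moves up and the 200 mg subject stays. The 200 mg column then holds 85 + 1 = 86 subjects and the placebo column 85 − 1 = 84. One of the 86 took only placebo, and no column counts that subject under placebo.

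**Step 3: size.** Let m of the 85 subjects in a dose arm take only placebo kits, with true event rates pa on drug and pp on placebo. The values of m, pa and pp are assumptions.

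- Expected rate shown = [(85 − m) × pa + m × pp] / 85
- Shortfall = m × (pa − pp) / 85

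| m | Share of arm | Shortfall at 30% v 20% | Shortfall at 10% v 2% | A 10-point excess shows as |
|---|---|---|---|---|
| 1 | 1.2% | 0.12 points | 0.09 points | 10 × 84/85 = 9.9 |
| 2 | 2.4% | 0.24 | 0.19 | 10 × 83/85 = 9.8 |
| 4 | 4.7% | 0.47 | 0.38 | 10 × 81/85 = 9.5 |
| 8 | 9.4% | 0.94 | 0.75 | 10 × 77/85 = 9.1 |

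One event that occurred on wrong placebo kits adds 1/85 = 1.18 points to the dose arm and 1/510 = 0.20 points to the pooled column (6 × 85 = 510).

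**Step 4: how many kits must be wrong.** Kits cover the time to the next visit (Protocol 8.5.4). In the first 12 weeks the kits dispensed at Baseline and Weeks 1, 2, 4 and 8 cover 1, 1, 2, 4 and 4 weeks. A single wrong Week 4 or Week 8 kit is 4/12 = 33% of the period. More than 50% needs at least two wrong kits, for example Weeks 4 and 8: 8/12 = 67%.

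**The case against.** The strongest reply is that this is a deliberate, prespecified choice: a general statement, then its limits, with a worst-case reason. Holding events in the higher-dose column is a recognisable conservative convention. That stands as a description of intent. It does not answer the denominator effect or the swap in Step 2, and it does not make the unqualified as-treated label in SAP 12.1.6 accurate.

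The second reply is that the errors can be traced. Listings show allocation discrepancies (16.2.1.1), dispensing mistakes by kit (16.2.5.3), exposure by subject (16.2.5.1 and 16.2.5.2) and every serious event (16.2.10.3). Subjects with deaths, serious events or discontinuations due to events are identified for narratives (16.2.10.7). This stands for the final report, although no planned table or sensitivity analysis reallocates the subjects.

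The third reply is that the effect is small. That stands. The tables up to Week 12 carry no p-values, and the planned q.d. versus b.i.d. tests concern efficacy and pharmacodynamics, not safety.

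A reader might infer three stronger things that the documents do not support:

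- **That an equal-dose swap can never be reassigned.** This depends on an undefined word. If dose meant dose per intake, a 50 mg b.i.d. subject who took 100 mg q.d. kits could count as higher.
- **That safety is generally attributed to a treatment not taken.** This is literal only when every kit was wrong; otherwise the randomised treatment was partly taken.
- **That one misplaced rare event shows a large bias.** With 1 or 2 serious events in an arm, one event more or less is a 50 to 100% change. That is small-number arithmetic under any allocation rule and does not measure this asymmetry.

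**Conclusion.** The point holds as a minor defect in a stated rule. SAP 2.4.1 announces allocation by treatment taken and then applies it upward only, so subjects with mostly or entirely lower-dose or placebo kits remain in the randomised higher-dose column. The equal-daily-dose case follows only if dose means total daily dose. That is how the SAP uses the word in its regimen model, but 2.4.1 does not say so.

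The effect on the tables is probably small: under one percentage point in an arm's rate for up to 8 wholly misallocated subjects of 85, at the rates assumed above. The documents give no count of kit errors. The result does not bear on the primary efficacy analysis, which is as-randomised. A conclusion that the safety tables are materially biased would not be supported.

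**What to change.** In SAP 2.4.1:

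1. Keep the present rule and apply it first: more than 20% wrong drug of a higher dose moves the subject to that higher dose.
2. Add: if more than 50% of the drug used in the period was a lower dose, placebo, or the other regimen at the same daily dose, assign the subject for safety to the treatment that made up the largest share of doses taken.
3. Define dose as total daily dose.
4. Keep the flag in Listing 16.2.1.1.

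A single symmetric rule, with a 20% trigger and assignment to the largest share, looks simpler but would be worse. A subject with 21 to 49% wrong higher-dose drug now moves up. Under that rule the assigned treatment would still be the largest share, so the subject would go back to the lower-dose column. One wrong Week 4 or Week 8 kit (33%) falls in that range.

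The cost is a few sentences and one extra derivation, and a few subjects may change column. The change is best made before unblinding.
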